addressing the transfer of acquired skills (e.g. UE motor capacity) to the performance of UE tasks during activities of daily living (ADL). The ALPS protocol will be relevant to clinical practice because it will provide clinicians with a structured, patient-centered motor learning approach to facilitate use of the paretic arm and hand. In addition, comparisons between our two intervention groups (robot-assisted therapy vs. robot-assisted therapy [RT] and task-oriented training [RT-TOT]) will add to our scientific knowledge of whether the combination of robot therapy and therapist-directed task-oriented training provides added benefit to RT alone. We will examine participant outcome measures across domains of the International Classification of Functioning (ICF)¹¹ to provide insights regarding mechanisms that underlie the recovery of motor function after stroke.

II. Specific Aims

The specific aims of this pilot study are:

Aim 1: To develop and refine a structured Active Learning Program for Stroke (ALPS) that integrates motor learning strategies with a patient-targeted home action plan to be used with either 1) robot-assisted therapy (RT) or 2) combined robot-assisted therapy and task-oriented training (RT-TOT) for the paretic arm and hand after stroke, in preparation for a larger clinical trial.

Hypothesis 1.1: RT and combined RT-TOT protocols that incorporate ALPS training will be feasible and well-tolerated by participants.

Hypothesis 1.2: After intervention, participants in both treatment groups will identify and implement a greater number of motor learning strategies during UE tasks in clinic and home settings and will report increased self-efficacy as measured by the Confidence in Arm and Hand Movement (CAHM) scale.

Aim 2: To examine effects of ALPS training and a patient-targeted home action plan combined with either 1) RT or 2) RT-TOT on paretic UE motor capacity and performance during daily activities, using *outcome measures across ICF domains*.

Hypothesis 2.1: Compared to RT alone, RT-TOT will yield similar outcomes on clinical measures of UE motor capacity (e.g. Fugl-Meyer Assessment, Wolf Motor Function Test), but greater gains on measures of UE function in the home and community (e.g. Motor Activity Log, UE accelerometry data via wearable sensors).

III. Subject Selection

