We will recruit up to 20 adults between the ages of 18 and 82 years and diagnosed with unilateral stroke more than 6 months prior to study enrollment. Stroke type will include both ischemic and hemorrhagic stroke. Eligible participants will be screened and enrolled in the study if they meet all inclusion and exclusion criteria. Protocol approval will be obtained from the SRH Institutional Review Board (IRB) and all participants will provide their informed consent prior to study participation.

Inclusion criteria:

- Moderate UE hemiparesis (i.e. some ability to move shoulder, elbow & hand and initial score on the Fugl-Meyer Assessment (FMA) between 21-50/66)

- Intact cognitive function to understand and actively engage in the ALPS robotic therapy procedures (Montreal Cognitive Assessment Score $\geq 26/30$)¹² during initial evaluation visit

Exclusion criteria:

- No more than moderate impairments in paretic UE sensation, passive range of motion, and pain that would limit ability to engage in therapy
- Increased muscle tone as indicated by score of ≥ 3 on the Modified Ashworth Scale;
- Hemispatial neglect or visual field loss measured by the symbol cancellation subtest on the Cognitive Linguistic Quick Test ¹³
- Aphasia sufficient to limit comprehension and completion of the treatment protocol
- Currently enrolled or has plans to enroll in other upper limb therapy/research during the study period
- Contraindications for robot-assisted therapy including recent fracture or skin lesion of paretic UE

IV. Subject enrollment

Recruitment Methods:

Potential subjects may be identified by the following sources:

- Printed flyers given to rehabilitation departments of local hospitals.
- Flyers posted in the outpatient clinics, therapy gyms and in public spaces inside and outside of the hospital.
- The Partners RSVP for health website.
- Contact with support groups and conferences.
- Research recruitment emails, for example Spaulding Rehabilitation Network Research Recruitment emails, and Social Medias.
- Contact to patients listed in the Partners Research Patient Data Registry (RPDR).
- Stroke Survivors who previously volunteered to be contacted about opportunities to participate in research studies at SRH may be contacted by phone by a study staff.
- Attending physicians and therapists may refer their stroke inpatients/outpatients to the study. We will provide the physicians with study flyers.

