digit for connection to the robotically controlled slide that guides movement. Each one hour session will include visually evoked games that provide active-assistive training of collective, sequential and individual flexion and extension of the digits as well as isometric flexion/extension contractions. Rest periods will be offered between games, as needed. Task challenge for each training device will be incrementally increased or decreased based on participant performance.

All participants will receive 1 hour sessions, 2-3x/week for 6-9 weeks (total 18 sessions), divided into two 9 session treatment blocks. The two treatment blocks will be given in order, with all participants receiving proximal training via Armeo@Spring during the first block followed by Amadeo distal training during block 2. All training sessions for one treatment block will be completed before proceeding to the next. The robot training sessions will follow standard protocols that provide highly repetitive movement training, and the number of games/repetitions completed in each session will be recorded. Participants may miss up to 3 appointments, and we will reschedule the following day or week at a time that is mutually convenient. Participants who miss 4 consecutive appointments may be removed from the study.

Active Learning Program for Stroke (ALPS): ALPS development and implementation will be based upon principles of experience dependent neuroplasticity as described by Kleim & Jones,⁹ empirical evidence from UE motor learning and task-oriented training programs for individuals with stroke,^{10,27,28} and a conceptual framework for integrating skill, capacity and motivation as described in multiple publications by Winstein et al.^{10,29,30} While principles of repetition, intensity, and specificity of training are active ingredients of the RT and RT-TOT protocols to improve motor capacity, other motor learning constructs have not been well-infused into prior robot training programs. These constructs will be implemented during RT and RT-TOT sessions and will be an integral component of the home action plan. Preliminary examples of protocol components are highlighted in Table 3 below.

Motor Learning Principles	Example
Use it or lose it ^{9,10,27}	Identify interfering and changeable impairments Provide targeted UE training based on individual's motor capacity
Saliency of training tasks ^{9,10}	Establish clear patient-centered goals

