The tasks selected for the home action plan (HAP) will be based on the participant's identified upper extremity (UE) goals and/or therapist input based on a) the current focus of robot therapy (i.e. shoulder/elbow, hand) and b) scores on the FMA key form. Because of this participant-centered approach there will be no core tasks included in every HAP, however, similarities may be observed across individuals. Participants will identify an UE task to be completed at home and the ALPS strategy or strategies they will use to facilitate performance weekly. A brief self-report questionnaire to collect ordinal data on ALPS strategy use, HAP performance, frequency, & perceived difficulty will be administered by research staff after every 3rd therapy session. Participant's engagement in the home action plan will be rated using a 3 point Likert type scale²⁹ and patient-targeted UE tasks will be updated as needed. A similar questionnaire will be administered during the follow-up assessment to gain information regarding the participant's engagement in home practice after formal therapy has ended. Participants will be instructed that completion of the HAP is voluntary and will not affect their therapy in any way. The intent of the HAP is to provide documentation of home carry-over. It is not designed to be a comprehensive home exercise program.

4) MAL Visit Days 22-23: End-of intervention outcomes assessment battery
(administered at discharge assessment after 18 treatment sessions) **Equip with Actical wearable sensors.**

The same assessment battery as the one performed at baseline will be re-administered.

5) MAL Visit Day 24 (Final Visit): Follow-up outcomes assessment battery
(administered at 1 month post-therapy) **Equip with Actical wearable sensors.**

The same assessment battery as the one performed at baseline will be re-administered, **except for** the Motion Capture and EMG analysis.

VI. Biostatistical Analysis

Separate repeated measures analyses of variance (2 group x 3 time points) will examine changes in scores for each outcome measure across a) baseline, b) discharge and c) follow-up assessments. Descriptive statistics will be used to compare key group characteristics, including age, hand dominance, side of lesion, and years of education. Group comparisons will be assessed by chi-square analyses for categorical data and t-tests for continuous data. The data collected from this pilot study may be used for a power analysis of a larger clinical trial.

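### Hypothesis 2.1 predicts similar motor capacity in the two groups, but the planned ANOVA tests only for a difference, so none of its results can show similarity

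*Combined protocol and SAP*

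**What the plan says.** Hypothesis 2.1 (Section II, Aim 2) makes two predictions of different kinds. For motor capacity, with the FMA and WMFT as examples: "Compared to RT alone, RT-TOT will yield similar outcomes on clinical measures of UE motor capacity". For daily use of the arm, with the Motor Activity Log and accelerometry as examples: "but greater gains on measures of UE function in the home and community". The first is a claim of no important difference; the second is a claim of superiority.

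Section VI treats both alike: "Separate repeated measures analyses of variance (2 group x 3 time points) will examine changes in scores for each outcome measure". It then adds: "Group comparisons will be assessed by chi-square analyses for categorical data and t-tests for continuous data". That sentence follows one about group characteristics, so it may concern baseline comparability only. If it also covers outcomes, it adds another difference test.

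Section III sets the size: "We will recruit up to 20 adults between the ages of 18 and 82 years". The documents give no sample-size calculation, alpha, SD, effect size, allocation ratio or expected dropout. Section V mentions minimal detectable change for the FMA, Motor Activity Log and Stroke Impact Scale. It gives no values, does not include the WMFT, and does not link the idea to Hypothesis 2.1.

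**The concern.** A claim of similarity needs a statement of how large a difference would still count as similar, and an interval or test that can rule out anything larger. The plan has neither. The only planned output that could be read as similar is a non-significant group-by-time term, and in a small study that result is expected whether or not the treatments differ.

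The introductory section says that the group comparison "will add to our scientific knowledge of whether the combination of robot therapy and therapist-directed task-oriented training provides added benefit to RT alone". For motor capacity, the planned output cannot tell an absence of added benefit from a study too small to detect one. The low power also works against the superiority half, so it makes only the capacity half easy to appear to confirm, not Hypothesis 2.1 as a whole.

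**Working it through.** The plan states no power or sample-size figure, so there is none to reproduce. The check asks what each possible ANOVA result says about similarity, and then how often a non-significant result would arise when a real difference exists.

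**Logic.** A significant group-by-time term is evidence against similar outcomes. A non-significant term means only that zero difference was not excluded. Neither supports the prediction, and this does not depend on the sample size.

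**Inputs.** From the documents: at most 20 participants, two groups, three time points. Assumed, because the documents are silent: 1:1 allocation (10 per group), two-sided alpha 0.05, no dropout in the main case, and 8 per group (20% loss) as a second case. Section V allows for some loss ("Participants who miss 4 consecutive appointments may be removed from the study") but gives no rate. No SDs are given, so differences are in units of the SD of change from baseline.

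**Step 1: t-test on change scores.** Power comes from the noncentral t distribution with 2n − 2 df and noncentrality d × √(n/2).

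| True difference d | Power, n = 10 (18 df) | Non-significant | Power, n = 8 (14 df) | Non-significant |
|---|---|---|---|---|
| 0.5 SD | 0.185 | 82% | 0.154 | 85% |
| 0.8 SD | 0.395 | 60% | 0.320 | 68% |
| 1.0 SD | 0.562 | 44% | 0.461 | 54% |

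With 10 per group, power reaches 50% at d = 0.93 and 80% only at d = 1.32.

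**Step 2: the planned 2 x 3 ANOVA.** The group-by-time F test was simulated with 40,000 draws per cell, change SD = 1, and the difference equal at discharge and follow-up. Two covariance patterns were used: compound symmetry without correction, and discharge and follow-up changes correlated 0.8 with Greenhouse-Geisser correction.

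| True difference | Power, n = 10 (two patterns) | Non-significant | Power, n = 8 (two patterns) | Non-significant |
|---|---|---|---|---|
| 0.5 SD | 0.181, 0.189 | 81-82% | 0.152, 0.158 | 84-85% |
| 0.8 SD | 0.406, 0.418 | 58-59% | 0.329, 0.340 | 66-67% |
| 1.0 SD | 0.592, 0.594 | 41% | 0.489, 0.488 | 51% |

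With no true difference and 10 per group, the rejection rate was 0.049 under both patterns, as it should be. If a 0.8 SD difference is present at discharge only, power is 0.409 or 0.446, so the term is non-significant 55-59% of the time. The ANOVA and the t-test agree closely: with 10 per group, non-significance is more likely than not for true differences up to about 0.9 SD.

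**Step 3: precision.** The 95% CI half-width for the difference in change is t(0.975, df) × √(2/n).
- n = 10: 2.101 × √0.2 = 0.94 SD
- n = 8: 2.145 × √0.25 = 1.07 SD

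These are for unadjusted change scores. A non-significant result would typically leave differences approaching 1 SD, in one or both directions, unexcluded.

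**Step 4: could a formal similarity test work here?** Two one-sided tests at 5% (90% CI wholly inside the margin), true difference zero, 10 per group, 400,000 draws: power is 0.1% for a 0.5 SD margin, 39% for 1.0 SD and 81% for 1.37 SD. For 80% power at a 0.5 SD margin, the normal formula gives 2 × ((1.645 + 1.282)/0.5)² = 68.5, so 69 per group (70 with the t distribution). The margins are illustrative, since the documents give none.

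**The case against.** The strongest reply is that this is a pilot. Its main purpose is to develop and refine a therapy protocol, Aim 2 only sets out to examine effects, and the one onward statistical use named is planning: "The data collected from this pilot study may be used for a power analysis of a larger clinical trial". Section VI sets no alpha or decision rule for any hypothesis and nowhere says that a non-significant term will count as similarity. On that reading, the word similar expresses a scientific expectation, and harm arises only if someone later misreads a p-value. Further, the low-power figures apply to every outcome in Table 1, and the fitted ANOVA would supply what is needed to form a CI.

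Much of this is fair. The plan does not commit the error in so many words, and pilot status keeps the point from being critical. The core problem is the type of test and the missing margin, not the sample size; the small number only raises the chance of a misleading result. A CI could indeed be derived from the same model, but neither a CI nor a criterion for judging it is planned.

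What does not stand is the inference that nothing needs changing. Similarity on capacity is part of a numbered hypothesis, Section VI is where the plan should say how it will be judged, and the analysis given there cannot judge it. The remedy asks for neither more participants nor an equivalence trial.

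**Conclusion.** The concern holds and should be fixed. The planned difference test cannot support the capacity half of Hypothesis 2.1 whatever it shows. With 10 per group, the result most easily mistaken for support occurs in roughly four of five trials when the true difference is 0.5 SD and in about two of five when it is 1.0 SD. The logical point needs no assumptions. The percentages rest on 1:1 allocation, two-sided 5% and complete data, and loss of participants raises them. They cannot be converted to FMA or WMFT points because the documents give no SDs. The superiority half is a difference claim that the ANOVA can address, although with the same low power.

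**What to change.** Reword the capacity half of Hypothesis 2.1 along these lines: *The pilot will estimate the RT-TOT minus RT difference in UE motor capacity (FMA, WMFT).* The superiority half can stay as it is.

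Add to Section VI: *For the FMA and WMFT, the baseline-adjusted RT-TOT minus RT difference at discharge and at follow-up will be reported with its 95% CI. A non-significant ANOVA term will not be read as similarity.* The interval makes the uncertainty visible and serves the planning of the larger trial. The same reporting could be extended to the Motor Activity Log and accelerometry.

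No equivalence test is needed. If the team still wishes to claim similarity, it needs a group-level margin for each measure, justified and fixed before outcome data are seen, with the 90% CI lying wholly inside it. Minimal detectable change should not be adopted as that margin by default: it describes change in an individual, and the protocol gives no value for it and does not mention one for the WMFT.

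The cost is one reworded clause and two sentences, with no new data or visits. The price is that the pilot will probably be unable to claim similarity, as Step 4 of the working shows.

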Eligible patients will contact or give permission to be contacted by study staff to obtain more information about the study and informed consent.

At the first point of contact (usually a phone call), study staff will administer a phone-screening questionnaire to see if subjects are eligible for the study. Potential subjects who are deemed eligible during this initial contact will be invited to attend an in-person screening to ensure that all inclusion and exclusion criteria are met. If a prospective subject fails this screening, he/she will be excluded from the study.

Informed consent will be obtained by study staff members who have completed the Partners Healthcare System's human subject protection educational requirements, and the CITI Program in Protection of Human Subjects, in compliance with all Federal regulations regarding such training. Prospective subjects will be interviewed to determine preliminary eligibility.

[figure not shown]
Informed consent will be obtained and subjects will be enrolled in the study prior to any clinical or laboratory testing. Subjects will be given a copy of the IRB approved consent form during the initial interview, and study staff will explain in detail the nature of the informed consent process, study purpose and procedures, time commitments, risks, potential benefits, treatment alternatives, rights as research participants, study staff contact information, confidentiality procedures, and arrangements for medical care provided in case of injury during the study. Subjects will be given adequate time to consider their decision and encouraged to ask questions, both during the initial interview and throughout the study. The subject's decision-making capacity and ability to give consent will be assessed by the PI ([name]) or [name], Research Coordinator/Manager in the Motion Analysis Lab at SRH, using the University of California at San Diego (UCSD) Brief Assessment of Capacity for Consent Questionnaire. The subject must demonstrate an understanding of the study, that it is research, and answer questions re: the risks and benefits involved in the procedures.

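### The first exclusion criterion is worded as a permitted ceiling, so read literally it excludes mild and moderate therapy-limiting impairment and lets severe impairment through

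*Combined protocol and SAP*

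**What the plan says.** Section III, Subject Selection, has two inclusion bullets and six exclusion bullets.

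The first exclusion bullet reads: "No more than moderate impairments in paretic UE sensation, passive range of motion, and pain that would limit ability to engage in therapy".

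The other five each name a disqualifying state:

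- Muscle tone: the wording begins "Increased muscle tone as indicated by score of", and the cut-off given is a Modified Ashworth value of at least 3.
- Neglect or vision: "Hemispatial neglect or visual field loss measured by the symbol cancellation subtest", taken from a named cognitive test.
- Language: "Aphasia sufficient to limit comprehension and completion of the treatment protocol".
- Other participation: present or intended involvement in different arm treatment or studies while this one runs.
- Safety on the devices: "Contraindications for robot-assisted therapy including recent fracture or skin lesion of paretic UE".

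The inclusion bullets require moderate hemiparesis, with "initial score on the Fugl-Meyer Assessment (FMA) between 21-50/66", and a Montreal Cognitive Assessment score of at least 26/30. Neither sets a limit on sensation, passive range of motion or pain.

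Section III enrols people who satisfy both lists. Section IV applies the same lists at the in-person screening and adds: "If a prospective subject fails this screening, he/she will be excluded from the study".

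**The concern.** A bullet under an exclusion heading should describe the person to be kept out. This one describes the person who may come in. Applied as an exclusion, it turns away people with the lesser degrees of therapy-limiting impairment and is silent on people with the greatest degree, which defeats the purpose stated in the bullet's own closing words.

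The bullet is an operative rule, because failing the in-person screening means exclusion. The study tests whether the two protocols are feasible and well tolerated (Hypothesis 1.1) and is meant to prepare for a larger trial (Aim 1). An eligibility rule that points the wrong way should not be carried forward into that trial.

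**Working it through.** The plan gives no figure to reproduce here. The check is a count, a literal application of the bullet, and a search for any reading or other text that would repair it.

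**Count (Section III).** 2 inclusion + 6 exclusion = 8 eligibility bullets. Of the 6 exclusion bullets, 5 name a disqualifying state and 1 states a ceiling (5 + 1 = 6). Of all 8, only that one names sensation, passive range of motion or pain.

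**Literal application.** The wording is ambiguous in two ways. The *and* joining the three domains may mean any one of them or all three together. The limiting qualifier may attach to all three domains or only to pain. That gives 2 × 2 = 4 readings. I applied the bullet as an exclusion to three profiles:

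| Profile (all impairments therapy-limiting) | *And* = any one domain | *And* = all three domains |
|---|---|---|
| Mild or moderate in all three domains | Excluded | Excluded |
| Severe in all three domains | Not excluded | Not excluded |
| Severe pain; moderate sensation and range | Excluded | Not excluded |

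Each cell is the same for both scopes of the qualifier, since every impairment in these profiles is taken to limit therapy. The first two rows come out the wrong way round under all four readings, so the reversal does not depend on either ambiguity. The third row does depend on the meaning of *and*.

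**Can one reading make the list consistent?** Suppose every bullet is a condition that a participant must satisfy, as the enrolment wording in Sections III and IV could suggest. The first bullet then works as a ceiling. But the other five would then require raised tone, neglect or visual field loss, aphasia, concurrent upper limb therapy or research, and a contraindication to robot therapy. If instead every bullet is a reason to exclude, those five work and the first is reversed. Neither reading fits all six.

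**Does other text correct it?** No. The bullet is not restated elsewhere. The pain and sensation subtests of the Fugl-Meyer Assessment appear in Table 1 only as outcome assessments. The Fugl-Meyer range, the Ashworth limit and the robot contraindications may remove some people with severe impairment, but none of them sets a limit on these three domains.

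**Do the two obvious repairs agree?** Not necessarily. Moved to the inclusion list, the bullet can be read as requiring every domain to be at or below the ceiling, so one severe domain disqualifies. Kept as an exclusion with its direction reversed, it can be read as requiring all three domains to be above the ceiling. The person in the third row would be ineligible under the first repair and eligible under the second.

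**The case against.** The strongest reply is that this is a drafting slip whose intent is plain. The closing words of the bullet show its purpose, no clinician would turn away mild impairment and admit severe impairment, and the loose enrolment wording shows that both lists were meant to be read for sense. The literal reading can be pushed to absurdity: if the qualifier covers only pain, the bullet might even catch people with normal sensation or range, though the word for impairment arguably presupposes that some is present. No one is shown to have been wrongly enrolled or refused, and a count of bullets does not measure an effect on the trial.

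Most of this stands as an argument about weight. The intent can probably be recovered, and the practical effect is likely small. It does not remove the mismatch, because the heading and the bullet still say opposite things. Knowing the intended direction also does not settle how mixed profiles are to be handled. The two ambiguities are missing detail and are not needed to establish the error; they matter because the bullet has to be reworded anyway.

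**Conclusion.** The criterion is wrong as written. One of six exclusion bullets runs opposite to its heading, and it is the only one of eight eligibility bullets that names these three domains. Severity is minor. Confidence is high for the mismatch in wording and does not extend to any effect on enrolment.

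The conclusion rests on reading the bullet as the exclusion its heading says it is. How many of the at most 20 participants might be affected cannot be estimated: the documents give no distribution of these impairments among candidates, and they do not show whether the wording was carried into the screening form. No sample size, power or error-rate figure depends on it.

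**What to change.** Reword this one bullet in Section III so that heading and text agree. Either move it to the inclusion list as a ceiling, or keep it as an exclusion with its direction reversed. In the same edit, state whether *and* means any one domain or all three together, and whether the limiting qualifier covers all three domains or only pain. Then check that the screening form, which is not in the documents, says the same. Which clinical threshold to use is for the sponsor, and none is proposed here.

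The cost is a short wording amendment and one check of a form. No change to the analysis is needed.
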